Attachment 1: Summary of RECIST Criteria Version 1.1

The following information was extracted from Section 3, Section 4, and Appendix I of the New response evaluation criteria in solid tumors: revised RECIST guideline (version 1.1) authored by Eisenhauer et al (2009). Refer to the European Journal of Cancer article (2009;45(2):228-247) for the complete publication.⁸

3. Measurability of tumor at baseline**3.1 Definitions**

At baseline, tumor lesions/lymph nodes will be categorized measurable or non-measurable as follows:

3.1.1 Measurable

Tumor lesions: Must be accurately measured in at least one dimension (longest diameter in the plane of measurement is to be recorded) with a *minimum* size of:

- 10 mm by CT scan (CT scan slice thickness no greater than 5 mm)

The following two methods of measure are not allowed in this protocol:

- 10 mm caliper measurement by clinical exam (lesions which cannot be accurately measured with calipers should be recorded as non-measurable)
- 20 mm by chest X-ray
- *Malignant lymph nodes:* To be considered pathologically enlarged and measurable, a lymph node must be ≥ 15 mm in short axis when assessed by CT scan (CT scan slice thickness recommended to be no greater than 5 mm). At baseline and in follow-up, only the short axis will be measured and followed. See also 'Baseline documentation of target and non-target lesions' in section 4.2 of the RECIST guideline for information on lymph node measurement.

3.1.2 Non-measurable

All other lesions, including small lesions (longest diameter < 10 mm or pathological lymph nodes with ≥ 10 to < 15 mm short axis) as well as truly non-measurable lesions. Lesions considered truly non-measurable include: leptomeningeal disease, ascites, pleural or pericardial effusion, inflammatory breast disease, lymphangitic involvement of skin or lung, and abdominal masses/abdominal organomegaly identified by physical exam that is not measurable by reproducible imaging techniques.

3.2 Specifications by methods of measurements**3.2.1 Measurement of lesions**

All measurements should be recorded in metric notation, using calipers if clinically assessed. All baseline evaluations should be performed as close as possible to the treatment start and never more than 4 weeks before the beginning of the treatment.

3.2.2 Method of assessment

The same method of assessment and the same technique should be used to characterize each identified and reported lesion at baseline and during follow-up. Imaging based evaluation should always be done rather than clinical examination.

4. Tumor response evaluation

4.1 Assessment of overall tumor burden and measurable disease

To assess objective response or future progression, it is necessary to estimate the *overall tumor burden at baseline* and use this as a comparator for subsequent measurements.

4.2 Baseline documentation of ‘target’ and ‘non-target’ lesions

When more than one measurable lesion is present at baseline all lesions up to a maximum of five lesions total (and a maximum of two lesions per organ) representative of all involved organs should be identified as *target lesions* and will be recorded and measured at baseline (this means in instances where patients have only one or two organ sites involved a *maximum* of two and four lesions respectively will be recorded). For evidence to support the selection of only five target lesions, see analyses on a large prospective database in the article by Bogaerts et al. (Reference #10 in Eisenhauer publication).

Target lesions should be selected on the basis of their size (lesions with the longest diameter), be representative of all involved organs, but in addition should be those that lend themselves to *reproducible repeated measurements*. It may be the case that, on occasion, the largest lesion does not lend itself to reproducible measurement in which circumstance the next largest lesion, which can be measured reproducibly, should be selected.

Lymph nodes merit special mention since they are normal anatomical structures, which may be visible by imaging even if not involved by tumor. As noted in Section 3, pathological nodes which are defined as measurable and may be identified as target lesions must meet the criterion of a short axis of ≥ 15 mm by CT scan. Only the short axis of these nodes will contribute to the baseline sum. The *short* axis of the node is the diameter normally used by radiologists to judge if a node is involved by solid tumor. Nodal size is normally reported as two dimensions in the plane in which the image is obtained (for CT scan this is almost always the axial plane; for MRI the plane of acquisition may be axial, sagittal or coronal). The smaller of these measures is the short axis. For example, an abdominal node which is reported as being 20 mm•30 mm has a short axis of 20 mm and qualifies as a malignant, measurable node. In this example, 20 mm should be recorded as the node measurement (See also the example in Fig. 4 in Appendix II of the Eisenhauer reference). All other pathological nodes (those with short axis ≥ 10 mm but < 15 mm) should be considered non-target lesions. Nodes that have a short axis < 10 mm are considered non-pathological and should not be recorded or followed.

A sum of the diameters (longest for non-nodal lesions, short axis for nodal lesions) for all target lesions will be calculated and reported as the *baseline sum diameters*. If lymph nodes are to be included in the sum, then as noted above, only the short axis is added into the sum. The baseline sum diameters will be used as reference to further characterize any objective tumor regression in the measurable dimension of the disease.

All other lesions (or sites of disease) including pathological lymph nodes should be identified as *non-target lesions* and should also be recorded at baseline. Measurements are not required and these lesions should be followed as ‘present’, ‘absent’, or in rare cases ‘unequivocal progression’ (more details to follow). In addition, it is possible to record multiple nontarget lesions involving the same organ as a single item on the case record form (e.g. ‘multiple enlarged pelvic lymph nodes’ or ‘multiple liver metastases’).

4.3 Response criteria

This section provides the definitions of the criteria used to determine objective tumor response for target lesions.

4.3.1 Evaluation of target lesions

Complete Response (CR): Disappearance of all target lesions. Any pathological lymph nodes (whether target or non-target) must have reduction in short axis to <10 mm.

Partial Response (PR): At least a 30% decrease in the sum of diameters of target lesions, taking as reference the baseline sum diameters.

Progressive Disease: At least a 20% increase in the sum of diameters of target lesions, taking as reference the smallest sum on study (this includes the baseline sum if that is the smallest on study). In addition to the relative increase of 20%, the sum must also demonstrate an absolute increase of at least 5 mm. (Note: the appearance of one or more new lesions is also considered progression).

Stable Disease (SD): Neither sufficient shrinkage to qualify for PR nor sufficient increase to qualify for progressive disease, taking as reference the smallest sum diameters while on study.

4.3.2 Special notes on the assessment of target lesions

Lymph nodes. Lymph nodes identified as target lesions should always have the actual short axis measurement recorded (measured in the same anatomical plane as the baseline examination), even if the nodes regress to below 10 mm on study. This means that when lymph nodes are included as target lesions, the ‘sum’ of lesions may not be zero even if complete response criteria are met, since a normal lymph node is defined as having a short axis of <10 mm. Case report forms or other data collection methods may therefore be designed to have target nodal lesions recorded in a separate section where, in order to qualify for CR, each node must achieve a short axis <10 mm. For PR, SD and progressive disease, the actual short axis measurement of the nodes is to be included in the sum of target lesions.

Target lesions that become ‘too small to measure’. While on study, all lesions (nodal and non-nodal) recorded at baseline should have their actual measurements recorded at each subsequent evaluation, even when very small (eg 2 mm). However, sometimes lesions or lymph nodes which are recorded as target lesions at baseline become so faint on CT scan that the radiologist may not feel comfortable assigning an exact measure and may report them as being ‘too small to measure’. When this occurs it is important that a value be recorded on the eCRF. If it is the opinion of the radiologist that the lesion has likely disappeared, the measurement should be recorded as 0 mm. If the lesion is believed to be present and is faintly seen but too small to measure, a default value of 5 mm should be assigned (*Note:* It is less likely that this rule will be used for lymph nodes since they usually have a definable size when normal and are frequently surrounded by fat such as in the retroperitoneum; however, if a lymph node is believed to be present and is faintly seen but too small to measure, a default value of 5 mm should be assigned in this circumstance as well). This default value is derived from the 5 mm CT slice thickness (but should not be changed with varying CT slice thickness). The measurement of these lesions is potentially non-reproducible; therefore providing this default value will prevent false responses or progressions based upon measurement error. To reiterate, however, if the radiologist is able to provide an actual measure, that should be recorded, even if it is below 5 mm.

Lesions that split or coalesce on treatment. When non-nodal lesions ‘fragment’, the longest diameters of the fragmented portions should be added together to calculate the target lesion sum. Similarly, as lesions coalesce, a plane between them may be maintained that would aid in obtaining maximal diameter measurements of each individual lesion. If the lesions have truly coalesced such that they are no longer separable, the vector of the longest diameter in this instance should be the maximal longest diameter for the ‘coalesced lesion’.

4.3.3 Evaluation of non-target lesions

This section provides the definitions of the criteria used to determine the tumor response for the group of non-target lesions. While some non-target lesions may actually be measurable, they need not be measured and instead should be assessed only qualitatively at the timepoints specified in the protocol.

Complete Response (CR): Disappearance of all non-target lesions and normalization of tumor marker level. All lymph nodes must be non-pathological in size (<10 mm short axis).

Non-CR/Non-progressive disease: Persistence of one or more non-target lesion(s) and/or maintenance of tumor marker level above the normal limits.

Progressive Disease: Unequivocal progression (see comments below) of existing non-target lesions. (*Note:* the appearance of one or more new lesions is also considered progression).

4.3.4 Special notes on assessment of progression of non-target disease

The concept of progression of non-target disease requires additional explanation as follows:

When the patient also has measurable disease. In this setting, to achieve ‘unequivocal progression’ on the basis of the non-target disease, there must be an overall level of substantial worsening in non-target disease such that, even in presence of SD or PR in target disease, the overall tumor burden has increased sufficiently to merit discontinuation of therapy. A modest ‘increase’ in the size of one or more non-target lesions is usually not sufficient to qualify for unequivocal progression status. The designation of overall progression solely on the basis of change in non-target disease in the face of SD or PR of target disease will therefore be extremely rare.

When the patient has only non-measurable disease. This circumstance arises in some Phase studies when it is not a criterion of study entry to have measurable disease. The same general concepts apply here as noted above, however, in this instance there is no measurable disease assessment to factor into the interpretation of an increase in non-measurable disease burden. Because worsening in non-target disease cannot be easily quantified (by definition: if all lesions are truly non-measurable) a useful test that can be applied when assessing patients for unequivocal progression is to consider if the increase in overall disease burden based on the change in non-measurable disease is comparable in magnitude to the increase that would be required to declare progressive disease for measurable disease: ie, an increase in tumor burden representing an additional 73% increase in ‘volume’ (which is equivalent to a 20% increase diameter in a measurable lesion). Examples include an increase in a pleural effusion from ‘trace’ to ‘large’, an increase in lymphangitic disease from localized to widespread, or may be described in protocols as ‘sufficient to require a change in therapy.’ If ‘unequivocal progression’ is seen, the patient should be considered to have had overall progressive disease at that point. While it would be ideal to have objective criteria to apply to non-measurable disease, the very nature of that disease makes it impossible to do so, therefore the increase must be substantial.

4.3.5 New lesions

The appearance of new malignant lesions denotes disease progression; therefore, some comments on detection of new lesions are important. There are no specific criteria for the identification of new radiographic lesions; however, the finding of a new lesion should be unequivocal: ie, not attributable to differences in scanning technique, change in imaging modality or findings thought to represent something other than tumor (for example, some ‘new’ bone lesions may be simply healing or flare of pre-existing lesions). This is particularly important when the patient’s baseline lesions show partial or complete response. For example, necrosis of a liver lesion may be reported on a CT scan report as a ‘new’ cystic lesion, which it is not.

A lesion identified on a follow-up study in an anatomical location that was not scanned at baseline is considered a new lesion and will indicate disease progression. An example of this is the patient who has visceral disease at baseline and while on study has a CT or MRI brain ordered which reveals metastases. The patient’s brain metastases are considered to be evidence of progressive disease even if he did not have brain imaging at baseline.

If a new lesion is equivocal, for example because of its small size, continued therapy and follow-up evaluation will clarify if it represents truly new disease. If repeat scans confirm there is definitely a new lesion, then progression should be declared using the date of the initial scan.

4.4.1 Timepoint response

It is assumed that at each protocol-specified timepoint, a response assessment occurs. Table 1 in this attachment provides a summary of the overall response status calculation at each timepoint for patients who have measurable disease at baseline.

When patients have non-measurable (therefore non-target) disease only, Table 2 in this attachment is to be used.

4.4.2 Missing assessments and inevaluable designation

When no imaging/measurement is done at all at a particular timepoint, the patient is not evaluable (NE) at that timepoint. If only a subset of lesion measurements are made at an assessment, usually the case is also considered NE at that timepoint, unless a convincing argument can be made that the contribution of the individual missing lesion(s) would not change the assigned timepoint response. This would be most likely to happen in the case of progressive disease. For example, if a patient had a baseline sum of 50 mm with three measured lesions and at follow-up only two lesions were assessed, but those gave a sum of 80 mm, the patient will have achieved progressive disease status, regardless of the contribution of the missing lesion.

4.4.3 Best overall response: all timepoints

The *best overall response* is determined once all the data for the patient is known.

Best response determination in studies where confirmation of complete or partial response IS NOT required: Best response in these studies is defined as the best response across all timepoints (for example, a patient who has SD at first assessment, PR at second assessment, and progressive disease on last assessment has a best overall response of PR). When SD is believed to be best response, it must also meet the protocol-specified minimum time from baseline. If the minimum time is not met when SD is otherwise the best timepoint response, the patient's best response depends on the subsequent assessments. For example, a patient who has SD at first assessment, progressive disease at second and does not meet minimum duration for SD, will have a best response of progressive disease. The same patient lost to follow-up after the first SD assessment would be considered inevaluable.

Target lesions	Non-target lesions	New lesions	Overall response
CR	CR	No	CR
CR	Non-CR/non-PD	No	PR
CR	Not evaluated	No	PR
PR	Non-PD or not all evaluated	No	PR
SD	Non-PD or not all evaluated	No	SD
Not all evaluated	Non-PD	No	NE
PD	Any	Yes or No	PD
Any	PD	Yes or No	PD
Any	Any	Yes	PD

CR = complete response; PR = partial response; SD = stable disease; PD = progressive disease; NE = not evaluable.

Table 2 - Timepoint response: patients with non-target disease only		
Non-target lesions	New lesions	Overall response
CR	No	CR
Non-CR/non-PD	No	Non-CR/non-PD ^a
Not all evaluated	No	NE
Unequivocal PD	Yes or No	PD
Any	Yes	PD
CR = complete response; PD = progressive disease; NE = not evaluable.		
a 'Non-CR/non-PD' is preferred over 'stable disease' for non-target disease since SD is increasingly used as endpoint for assessment of efficacy in some studies so to assign this category when no lesions can be measured is not advised.		

Attachment 2: ECOG PS Grade Scale**ECOG Grade Scale (with Karnofsky conversion)**

- | | |
|---|---|
| 0 | Fully active, able to carry on all predisease performance without restriction. (Karnofsky 90-100) |
| 1 | Restricted in physically strenuous activity but ambulatory and able to carry out work on a light or sedentary nature, eg, light housework, office work. (Karnofsky 70-80) |
| 2 | Ambulatory and capable of all self-care but unable to carry out any work activities. Up and about more than 50% of waking hours. (Karnofsky 50-60) |
| 3 | Capable of only limited self-care; confined to bed or chair more than 50% of waking hours. (Karnofsky 30-40) |
| 4 | Completely disabled. Cannot carry on any self-care. Totally confined to bed or chair. (Karnofsky 10-20) |
| 5 | Dead. (Karnofsky 0) |

Attachment 3: Additional Information on CYP450 Drug Interactions

<http://www.fda.gov/drugs/developmentapprovalprocess/developmentresources/druginteractionslabeling/ucm093664.htm>

<http://medicine.iupui.edu/clinpharm/ddis/table.aspx>

Attachment 4: Anticipated Events

An anticipated event is an adverse event (serious or non-serious) that commonly occurs as a consequence of the underlying disease or condition under investigation (disease-related) or background regimen. For the purposes of this study the following events will be considered anticipated events:

Disease-specific Events

cauda equina syndrome

erectile dysfunction

haemospermia

haematuria

incontinence

lymphoedema

nocturia

painful ejaculation

pathological fracture

pollakiuria

prostate-specific antigen increased

spinal cord compression

urinary hesitation

ureteral obstruction

urethral obstruction

urinary flow decreased

urinary retention

urinary tract obstruction

ADT-related Events

depression

gynaecomastia

hot flush

libido decreased

osteoporosis

sexual dysfunction

testicular atrophy

Reporting of Anticipated Events

All AEs will be recorded in the eCRF regardless of whether considered to be anticipated events and will be reported to the sponsor as described in Section 12.3.1. Any anticipated event that meets serious criteria will be reported to the sponsor as described in Section 12.3.2. Each anticipated event will be assessed by the investigator at the individual case level and if considered to be drug-related will undergo expedited reporting (if appropriate) as per applicable clinical trial legislation to Health Authorities and IRB/ECs. (Note: Japan will not identify anticipated events for the Health Authorities). If an anticipated event is considered disease-related or not related to study drug the event will be exempt from expedited reporting. To meet US regulatory clinical trial legislation, the sponsor will perform aggregate review of anticipated events as outlined below, and if determined to be drug-related will implement expedited reporting of these events to Health Authorities and IRBs/ECs. If an interim analysis of trial results leads to an unblinded, aggregate review of safety data by the study team, the sponsor may terminate the review of pre-specified anticipated events outlined above.

Safety Assessment Committee (SAC)

A safety assessment Committee (SAC) will be established to perform reviews of pre-specified anticipated events at an aggregate level. The SAC is a safety committee within the sponsor's organization that is independent of the sponsor's study team. The SAC will meet to aid in the recommendation to the sponsor's study team as to whether there is a reasonable possibility that an anticipated event is related to the study intervention based on a review of the aggregate data by arm.

Statistical Analysis

Details of statistical analysis of anticipated events, including the frequency of review and threshold to trigger an aggregate analysis of anticipated events will be provided in a separate Anticipated Events Safety Monitoring Plan (ASMP).

Attachment 5: Leuprolide PK Sub-study

- To participate in this optional PK sub-study, subjects must consent to the PK sub-study indicating their willingness to participate.
- Optional PK samples will be collected from at least 60 consenting subjects (in selected countries) who received or will receive leuprolide acetate as the GnRH analog at the time of randomization. The subjects participating in this sub-study do not need to be the same subjects who provide trough PK samples for apalutamide (see Section 9.3).
- Samples will be collected on Day 1 of Cycles 1, 3, 4, 5, and 6 for analysis of leuprolide acetate concentrations and testosterone (see Laboratory Manual for details on sample collection).
- Samples should be collected prior to on-site study drug (ie, apalutamide) administration.
- Samples must be collected prior to leuprolide acetate administration if the injection is scheduled to be given on the same day.
- Testosterone samples to be collected from this sub-study will be analyzed using an ultrasensitive assay (see Laboratory Manual for details).
- Eligibility criteria for inclusion in this sub-study include the following:
 - Subjects must receive intramuscular or subcutaneous leuprolide acetate and must have received the first dose at least 21 days prior to randomization. The 11.25 mg, 22.5 mg, 30 mg, and 45 mg dosages are permitted.
 - Subjects must have no planned adjustment in the dose or frequency of leuprolide acetate administration during Cycles 1 to 6.
- For the analysis of leuprolide concentrations, to ensure that the PK samples are reflective of leuprolide concentrations at steady-state, blood samples collected within 21 days after the leuprolide injection may be excluded from the PK analysis.
- Descriptive statistics of leuprolide PK data will be summarized by treatment group and dose of leuprolide acetate. Statistical analysis comparing leuprolide concentrations when administered alone versus in combination with apalutamide will be performed. The percentage of subjects with testosterone concentrations <50 ng/dL) will also be summarized descriptively by treatment group. The results of these analyses will be provided in a separate report.

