2. OBJECTIVES AND HYPOTHESIS

2.1. Objectives

Primary Objective

The primary objective is to determine if the addition of apalutamide to ADT provides superior efficacy in improving radiographic progression-free survival (rPFS) or OS for subjects with mHSPC.

Secondary Objectives

- To evaluate clinically relevant improvements with addition of apalutamide to ADT including delays in pain progression and opioid use for prostate cancer, skeletal-related events (SREs), and the need for cytotoxic chemotherapy
- To characterize the safety of adding apalutamide to ADT in subjects with mHSPC
- To characterize the population pharmacokinetics (PK) and pharmacodynamics (PD) of apalutamide
- To evaluate the concentration of leuprolide and assess the PD effect of leuprolide on testosterone concentrations when used alone or in combination with apalutamide
- To evaluate the treatment effectiveness with the addition of apalutamide to ADT for the subpopulations of subjects with low-volume or high-volume mHSPC

Other Objectives

- To evaluate exploratory biomarkers predictive of response and resistance to treatment
- To evaluate patient relevant outcomes including symptoms (ie, pain, fatigue, urination) and function (ie, physical, emotional, social) and health-related quality of life
- To evaluate improvements in other clinically relevant endpoints with the addition of apalutamide to ADT
- To collect medical resource utilization (MRU) data that may be used in future economic modeling (the construction and reporting of the economic model will be conducted separately from this study)

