5. TREATMENT ALLOCATION AND BLINDING

Treatment Allocation

Procedures for Stratification and Randomization

Subjects will be stratified by Gleason score at diagnosis (≤ 7 versus >7), region (North America [NA] and European Union [EU] versus Other Countries), and prior docetaxel use (Yes versus No). Subjects will be randomly assigned to the active or control group in a 1:1 ratio. The randomization will be balanced by using randomly permuted blocks. The interactive web response system (IWRS) will assign a unique treatment code, which will dictate the treatment assignment and matching study drug kit for the subject. The requestor must use his own user identification and personal identification number when contacting the IWRS, and will then give the relevant subject details to uniquely identify the subject.

Blinding

The investigator will not be provided with randomization codes. The codes will be maintained within the IWRS, which has the functionality to allow the investigator to break the blind in the event of an emergency for an individual subject.

Under normal circumstances, the blind should not be broken until completion of the study or the IDMC recommendation for unblinding is accepted by the sponsor. Otherwise, the blind should be broken only if the specific course of action for a safety issue would be dictated by knowing the treatment status of the subject. In such cases, the investigator may in an emergency determine the identity of the treatment by contacting the IWRS. It is recommended that the investigator contact the sponsor or its designee if possible to discuss the particular situation, before breaking the blind. Telephone contact with the sponsor or its designee will be available 24 hours per day, 7 days per week. In the event the blind is broken, the sponsor must be informed as soon as possible. The date, time, and reason for the unblinding must be documented by the IWRS, in the appropriate section of the electronic case report form (eCRF), and in the source document. The documentation received from the IWRS indicating the code break must be retained with the subject's source documents in a secure manner.

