## **7. PHARMACOKINETICS**

Pharmacokinetic assessment (trough PK samples) will be conducted. Pre-dose blood samples for analysis of apalutamide and the active metabolite JNJ-56142060 concentrations will be collected on Day 1 of Cycles 2, 3, 4, 5, and 6.

Descriptive statistics including mean and geometric mean values will be summarized.

Pharmacokinetic samples will be collected from at least 60 subjects who received or will receive leuprolide acetate as the GnRHa at the time of randomization. Samples will be collected on Day 1 of Cycles 1, 3, 4, 5, and 6 for analysis of leuprolide and testosterone concentrations.

Descriptive statistics of leuprolide PK data will be summarized by treatment group and dose of leuprolide acetate. Statistical analysis comparing leuprolide concentrations when administered (with placebo) alone versus in combination with apalutamide will be performed. The percentage of subjects with testosterone concentrations <50 ng/dL) will also be summarized descriptively by treatment group.

The results of these analyses will be provided in a separate report.

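### In the leuprolide sub-study the only stated testosterone analysis is a descriptive percentage below 50 ng/dL, and the leuprolide comparison leaves scale, visits and use of the Cycle 1 value unspecified

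*Protocol*

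**What the plan says.** Protocol Section 2.1 lists as a secondary objective "To evaluate the concentration of leuprolide and assess the PD effect of leuprolide on testosterone concentrations when used alone or in combination with apalutamide". The objective has two parts, and the second is worded in terms of testosterone concentrations.

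Attachment 5 gives the design. At least 60 consenting subjects in selected countries are sampled for leuprolide and testosterone on Day 1 of Cycles 1, 3, 4, 5 and 6. On timing it says "Samples should be collected prior to on-site study drug (ie, apalutamide) administration", so the Cycle 1 sample precedes the first dose of apalutamide or placebo. Participants must have had their first leuprolide dose at least 21 days before randomization. Four leuprolide strengths are permitted. Testosterone is measured with an ultrasensitive assay.

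Three analyses are stated:

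- Descriptive leuprolide summaries. SAP Section 7: "Descriptive statistics of leuprolide PK data will be summarized by treatment group and dose of leuprolide acetate".
- A leuprolide comparison. Attachment 5: "Statistical analysis comparing leuprolide concentrations when administered alone versus in combination with apalutamide will be performed". SAP Section 7 repeats this and makes clear that alone means with placebo.
- The percentage of subjects with testosterone below 50 ng/dL, descriptively, by arm.

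On sample handling, Attachment 5 adds that "blood samples collected within 21 days after the leuprolide injection may be excluded from the PK analysis". That sentence concerns the leuprolide analysis only. Results go to a separate report.

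**The concern.** The design collects more than the stated analysis is said to use. An ultrasensitive assay resolves differences well below 50 ng/dL, but the only named testosterone output records which side of 50 each man falls on. In men treated with leuprolide for at least three weeks, that proportion is likely to sit near its ceiling in both arms. The sub-study could then report two almost identical percentages and leave the testosterone part of the objective largely unanswered.

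For leuprolide, each man supplies a concentration measured before apalutamide. Neither document says whether the comparison uses it, which visits count, or whether concentrations are analysed on the log scale. With so small a sample these choices affect what can be detected, and leaving them open until the data are seen weakens the result. The main trial's conclusions on rPFS, OS and safety are not at stake.

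**Working it through.** **Inputs from the documents.** At least 60 subjects (Attachment 5). Allocation: "Subjects will be randomly assigned to the active or control group in a 1:1 ratio" (Protocol Section 5), so about 60/2 = 30 per arm; sub-study participation is not a stratification factor, so an even split is an assumption. Four permitted strengths, so 60/(2 × 4) = 7.5 men per arm-by-strength cell on average. General two-sided level 0.05 (SAP Section 5.1.1). The documents give no SD, effect size, margin or power for the sub-study, so there is no planned figure to reproduce.

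**Assumptions, shown as ranges.** Testosterone log-normal with median 8 to 15 ng/dL and log-SD 0.5 to 0.7; leuprolide CV 30% to 80%; correlation between the Cycle 1 and later log values 0.3 to 0.8. Powers below use 30 per arm and one value per man.

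**1. Precision of the percentage.** The exact lower 95% limit for 30/30 is 0.025^(1/30) = 0.884, giving 88.4% to 100%. For 29/30 the interval is 82.8% to 99.9%.

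**2. Power near the ceiling.** For true proportions of 97% and 90%, Fisher's exact test has 3% power (normal approximation 19%); 80% power would need 194 per arm by the normal approximation. For 99% against 80%, Fisher power is 48%.

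**3. The same testosterone shift, cut at 50 or kept continuous.** With median m and log-SD s, the proportion below 50 is Φ[(ln 50 − ln m)/s]. On the log scale, power is Φ[ln(ratio)/(s√(2/30)) − 1.96]. For a doubling:

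| Median, log-SD | % below 50, before → after doubling | Fisher power on % | Power on log concentration |
|---|---|---|---|
| 8, 0.5 | 99.99 → 98.9 | about 0% | >99% |
| 10, 0.7 | 98.9 → 90.5 | 4.5% | 97% |
| 15, 0.5 | 99.2 → 84.7 | 26% | >99% |
| 15, 0.7 | 95.7 → 76.7 | 41% | 97% |

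For the 10, 0.7 row on the log scale: 0.693/(0.7 × 0.258) − 1.96 = 1.88, so power is 97%. Over all combinations tried, a doubling gives 0% to 41% on the percentage and at least 97% on the log scale. A 1.5-fold rise gives 0% to 6% against 61% to 88%.

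**4. Leuprolide: value of the Cycle 1 sample.** Adjusting for it multiplies the residual variance by 1 − ρ²: 0.91, 0.75, 0.51 and 0.36 at ρ = 0.3, 0.5, 0.7 and 0.8, a reduction of 9% to 64%. With log-SD = √ln(1 + CV²), power for a concentration ratio of 0.75 is:

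| CV | Unadjusted | Adjusted, ρ = 0.7 |
|---|---|---|
| 30% | 97% | >99% |
| 50% | 66% | 91% |
| 80% | 35% | 60% |

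A simple change score has variance 2(1 − ρ) relative to no adjustment: 1.4 at ρ = 0.3 and 0.6 at ρ = 0.7. It helps only when ρ exceeds 0.5, so covariate adjustment is the safer form.

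**The case against.** The strongest reply is that little here is decided wrongly; it is simply not spelled out. Both documents define baseline generally (Protocol Section 9.1.3; SAP Section 2), and those definitions cover the Cycle 1 Day 1 sample. A reader might infer that the plan discards this sample as a baseline. The documents do not say so; they are silent on its use. That silence still matters: separate analysis plans are promised for the PRO data (SAP Section 5.5.3) and for biomarkers (Protocol synopsis), but for leuprolide only a separate report.

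A reader might also infer that Cycle 1 samples would be pooled into the apalutamide group's data and dilute the contrast. No section describes such pooling, and a sample taken before the first dose is not a combination sample.

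Nor do the documents support reading the arm comparison as distorted by leuprolide strength or injection timing. Assignment is randomized, so apart from optional participation and discretionary exclusions these add noise rather than bias. Attachment 5 also limits the noise: a sample due on an injection day is drawn before the injection, and no change in leuprolide dose or frequency may be planned during Cycles 1 to 6.

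Finally, the percentage below 50 ng/dL is a legitimate check that castrate levels are maintained, and a large loss of suppression could show in it. It would be too strong to say that it can reveal nothing; the gap is that it stands alone. No testosterone threshold applies at entry, so the ceiling is probable, not established.

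**Conclusion.** The point holds as a minor one. Its firmer half is testosterone: an objective about concentrations, measured with a sensitive assay and with a value before study drug, has one dichotomised descriptive output with little power to show a change at about 30 per arm. The interval for 30/30 needs no distributional assumption; the comparison with a log-scale analysis rests on the assumed castrate-range distributions.

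The leuprolide half is a gap in pre-specification. Its cost is precision, and the size depends on a correlation that the documents do not give: small at 0.3, substantial at 0.7 or above. No figure in either document is contradicted. The sub-study is optional, carries no allocated alpha, and does not bear on the trial's primary conclusions.

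**What to change.** In Attachment 5 and SAP Section 7:

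- Analyse log testosterone and log leuprolide at Cycles 3 to 6 in a repeated-measures model with treatment, the Cycle 1 Day 1 value, leuprolide strength and time since the last injection. Report geometric mean ratios with confidence intervals.
- Keep the percentage below 50 ng/dL, by visit, as a descriptive line.
- State in advance how leuprolide samples within 21 days of an injection are handled, in place of the present discretion, including what happens when the Cycle 1 value is affected or missing.
- State the precision that 60 subjects provide.

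The cost is wording. The samples are already planned, GnRH analog treatment is documented in the eCRF (Protocol Section 6.2), and the 21-day rule already presupposes injection dates. There is a small downside: some men may lack a usable baseline, for example if a repeat injection falls shortly before Cycle 1, and for others Cycle 1 may fall in the first injection interval. Time since injection as a covariate and a stated missing-baseline rule deal with most of this.
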